3.5 STUDY CALENDAR

Procedures	Baseline Screening ⁶	Every Cycle (within 3 days)	Every 2 Cycles (within 3 days)	Off Treatment Evaluations (Following Treatment) ⁵				
				1 Month	3 Months	6 Months	12 Months	FU
Confirmation of thyroid cancer	X							
Informed Consent	X							
History and PE including height and weight	X							
Limited PE		X		X	X	X	X	
Vital signs	X	X						
Performance Score ECOG	X	X		X	X	X	X	
Toxicity evaluation	—————→							
12L ECG	X	X				X		
RECIST 1.1 disease assessment	X		X					
Urinalysis	X	X						
CBC with diff and platelets	X	X		X	X	X	X	
Chemistries ¹	X	X		X	X	X	X	
TSH and Thyroglobulin	X	X						
Serum or urine beta-HCG	X							
CT CAP or MRI	X		X	X	X	X	X	
Brain MRI or CT Scan	X							
Bone Scan	X							

Procedures	Baseline Screenin g ⁶	Every Cycle (within 3 days)	Every 2 Cycles (within 3 days)	Off Treatment Evaluations (Following Treatment) ⁵				
				1 Mont h	3 Mont hs	6 Mont hs	12 Mon ths	FU
Tumor Biopsy	X							
FDG PET Scan ²	X		X					
Phone/Email Evaluation ³								X
Advance Directives ⁴	X							

¹ Sodium (Na), Potassium (K), Chloride (Cl), Total CO2 (bicarbonate), Creatinine, Glucose, Urea nitrogen (BUN), Albumin, Calcium total, Alkaline Phosphatase, ALT/GPT, AST/GOT, Total Bilirubin, Total Protein, cortisol, PT/PTT

² 18F FDG PET scan will be performed after 2 cycles of treatment (+/- 3 days), and then annually or when clinical indicated.

³ Following the 12-month evaluation patients will be followed via phone or e-mail contact every 6 months for survival

⁴ Filling out of the advance directives will be offered, but obtaining of it is not required. For details see Section **10.3**

⁵ For follow up visits +/- window applies: +/- 1 week for 1 Month, +/- 2 weeks for 3 Month, +/- 4 weeks for 6 and 12 Months.

⁶ Evaluations done at screening will be used as Baseline assessments.

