2 ELIGIBILITY ASSESSMENT AND ENROLLMENT

2.1 ELIGIBILITY CRITERIA

2.1.1 Inclusion Criteria:

- 2.1.1.1 Subjects \geq 18 years of age.
- 2.1.1.2 Thyroid cancer histology or cytology that is aggressive (anaplastic/undifferentiated thyroid cancer, poorly differentiated thyroid cancer, hürthle cell carcinoma, tall-cell variant of papillary thyroid cancer, sclerosing variant of papillary thyroid cancer).
- 2.1.1.3 Measurable disease.
- 2.1.1.4 Eastern Cooperative Oncology Group (ECOG) performance status of 0 to 2.
- 2.1.1.5 Absolute neutrophil count \geq 1,000/ μ L
- 2.1.1.6 Platelets \geq 75,000/ μ L
- 2.1.1.7 Creatinine \leq 1.5x upper limit of normal (ULN) or creatinine clearance \geq 60ml for

- patients with creatinine levels 1.5 times above institutional ULN (calculated based on age, weight and sex)
- 2.1.1.8 Total bilirubin $\leq 1.5x$ ULN; AST/ALT $\leq 2.5x$ ULN. For subjects with documented liver metastases, the AST/ALT may be $\leq 5x$ ULN.
 - 2.1.1.9 Recovery to Grade 1 or baseline of any toxicity due to prior anticancer therapies (excluding alopecia).
 - 2.1.1.10 Platelet transfusions to help patients meet eligibility criteria are not allowed within 3 days prior to screening CBC or Cycle 1, Day 1 treatment.
 - 2.1.1.11 Women of child bearing potential must have a negative serum pregnancy test.
 - 2.1.1.12 The effects of CUDC-907 on the developing human fetus are unknown. For this reason, women of child-bearing potential and men must agree to use adequate contraception (hormonal or barrier method of birth control; abstinence) prior to study entry, for the duration of study participation and for 30 days following the last study treatment. Should a woman become pregnant or suspect she is pregnant while she or her partner is participating in this study, she should inform her treating physician immediately.
 - 2.1.1.13 Able to provide written informed consent and to follow protocol requirements.
- 2.1.2 Exclusion Criteria:
- 2.1.2.1 Systemic anticancer therapy within 4 weeks of study entry, except for subjects with anaplastic/undifferentiated thyroid cancer who may be enrolled immediately after discontinuation of previous therapy.
 - 2.1.2.2 Other investigational agents within 4 weeks prior to study treatment, except for subjects with anaplastic/undifferentiated thyroid cancer who may be enrolled immediately of discontinuation of previous therapy.

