2.2.4 Within 3 days prior to treatment

- Serum or urine beta-HCG (woman of childbearing potential)

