3.4 EVALUATION DURING TREATMENT

Laboratory evaluations and physical examinations will be performed within two weeks prior to initial treatment and every three weeks (one cycle) while subjects are on therapy.

- CBC with differential and platelets
- Chemistries: Sodium (Na), Potassium (K), Chloride (Cl), Total CO₂ (bicarbonate), Creatinine, Glucose, Urea nitrogen (BUN), Albumin, Calcium total, Alkaline Phosphatase, ALT/GPT, AST/GOT, Total Bilirubin, Total Protein, cortisol, PT/PTT, TSH and thyroglobulin.
- Urinalysis

Within three days prior to each treatment cycle.

- Toxicity evaluation
- Vital signs, ECOG status, 12 L ECG

Abbreviated Title: CUDC-907 for thyroid cancer
Version Date: 10/11/2017

- Limited Physical examination

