3.6 CRITERIA FOR CONTINUED TREATMENT

3.6.1 Prior to each treatment cycle.

- Treatment with CUDC-907 will continue until progression of disease, development of unacceptable toxicity, or withdrawal of consent.
- Adequate hematologic and organ function:
 - Hemoglobin greater than or equal to 8.0 gm/dL; ANC greater than or equal to 1,000/mm³; Platelets greater than or equal to 75,000/mm³
 - Creatinine \leq 1.5x upper limit of normal (ULN)
 - Total bilirubin \leq 1.5x ULN
 - AST/ALT \leq 2.5x ULN. For subjects with documented liver metastases, the AST/ALT may be \leq 5x ULN.

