3.7 RESTAGING

Patients will undergo the following evaluations at the end of every 2 cycles of treatment (+/- 3 days).

- CT scan of the chest, abdomen and pelvis (CT C/A/P) or MRI
- ¹⁸F FDG PET scan will be performed after 2 cycles of treatment (+/- 3 days), and then annually or when clinical indicated.
- Patients who continue to receive clinical benefit may continue treatment at the discretion of the PI.
- Response will be determined using RECIST 1.1 criteria (please see Section 6.4)

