10.1.13 Pregnancy and Lactation

There are no data available on the effect of CUDC-907 on the developing fetus. It is not known whether CUDC-907 is excreted in human milk.

Subjects who are pregnant or who intend to become pregnant during the treatment period should not receive CUDC-907. Men and women of childbearing potential and their partners must use an effective method of contraception during the treatment period and for 30 days following the last study treatment for subjects receiving CUDC-907. Adequate contraception is defined as hormonal birth control, intrauterine device, double barrier method or total abstinence.

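### Beta-HCG is scheduled only before the first dose of an open-ended treatment, so an early on-treatment pregnancy could go unrecognised for one or more cycles

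*Combined protocol and SAP*

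**What the plan says.** Section 2.2.4 asks for a serum or urine beta-HCG in women of childbearing potential in the 3 days before treatment. The calendar in section 3.5 has a row for "Serum or urine beta-HCG" that is marked under baseline screening and nowhere else.

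On duration, section 3.6.1 states: "Treatment with CUDC-907 will continue until progression of disease, development of unacceptable toxicity, or withdrawal of consent". Cycles are 21 days (section 3.1), and no maximum number is set.

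On fetal risk, section 10.1.13 states: "There are no data available on the effect of CUDC-907 on the developing fetus". The safeguards during treatment are these:

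- Contraception. Section 10.1.13: "Men and women of childbearing potential and their partners must use an effective method of contraception during the treatment period". This extends to 30 days after the last dose.
- Self-report. Section 2.1.1.12: "Should a woman become pregnant or suspect she is pregnant while she or her partner is participating in this study", she is to tell her physician at once.
- Action once pregnancy is known. It is an off-treatment criterion (3.9.1), and section 7.3.1.1 requires immediate discontinuation, with the sponsor informed within 24 hours of the investigator becoming aware.

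**The concern.** The stopping and reporting rules can act only after someone knows that the woman is pregnant, and nothing scheduled after the first dose looks for pregnancy. Contraception lowers the chance of conception but does not detect it. Self-report depends on the woman suspecting a pregnancy, and that may come late, because fatigue and nausea are among the drug's commonest effects and can resemble early pregnancy.

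What is at stake is patient and fetal safety. Dosing could continue through an unrecognised early pregnancy, as could the imaging due after cycle 2: "CT scan of the chest, abdomen and pelvis (CT C/A/P) or MRI" plus FDG PET (section 3.7). The response endpoint and the two-stage design are not affected.

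**Working it through.** The plan gives no figure to reproduce. The check sets the schedule sections side by side and then sizes the exposure.

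**1. Where a pregnancy test appears**

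| Section | Beta-HCG listed? |
|---|---|
| 2.2.4 screening | Yes, once |
| 3.4 evaluation during treatment | No (blood counts, chemistries, urinalysis, ECG, examination) |
| 3.5 calendar | Baseline column only |
| 3.6.1 criteria before each cycle | No |
| 3.7 restaging | No |
| 3.8 visits at 3, 6 and 12 months | No |
| 3.9 safety visit about 30 days after last dose | No |

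The calendar and the section text agree, so the empty cells are not a table-reading fault. A woman treated for k cycles has one test before cycle 1 and none at the k − 1 later cycle starts.

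**2. Exposure per unrecognised pregnancy**

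Inputs: 5/2 schedule, 60 mg, 21-day (3-week) cycle (sections 3.1 and 3.2); 4/3 as the first reduction step (Table 3).

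- Full dose: 5 × 3 = 15 doses per cycle (15 × 60 mg = 900 mg); 2 × 15 = 30 doses by the first restaging.
- On 4/3: 4 × 3 = 12 doses per cycle; 2 × 12 = 24 by the first restaging.

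These are doses given if a pregnancy beginning soon after the baseline test is not recognised over that period. The documents do not say how long recognition would take.

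**3. Interval between tests**

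As written, the interval is the whole treatment period. With a test in the 3 days before every cycle, the longest gap runs from 3 days before one cycle to the first day of the next: 21 + 3 = 24 days, if cycles are not delayed.

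**4. Expected number of pregnancies**

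The documents give only the accrual ceiling of 50 (section 8). The inputs below are assumptions. Formula: women of childbearing potential × years on drug × annual contraceptive failure rate.

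- Low: 5 × 0.25 × 0.01 = 0.0125
- High: 15 × 0.5 × 0.05 = 0.375
- High with one year on drug: 15 × 1 × 0.05 = 0.75

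**5. Symptom overlap**

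Table 2 (section 1.2): fatigue (16 + 1)/44 = 39%; nausea 11/44 = 25%. Section 11.1.12 also names both among the most frequent events in each of the two studies it summarises.

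**6. Timing of the safety visit**

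30 ± 7 days (calendar footnote 5) gives about days 23 to 37 after the last dose.

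**The case against.** The strongest reply is that this is a preference about safeguards rather than an error. The schedule is internally consistent, and nothing in the protocol promises testing on treatment. Fetal risk is covered in layers: a negative test at entry, contraception with a named list of accepted methods, self-report, mandatory stopping and fast notification. Each cycle also brings a toxicity evaluation and a limited physical examination, at which a clinician can ask about pregnancy and order a test. That stands as context, but all of it depends on someone raising the question; no scheduled step detects a pregnancy nobody suspects.

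Second, the numbers are small and assumed. Even the extreme case is below one pregnancy in the trial, and the relevant count is smaller still: only pregnancies that self-report would miss and a per-cycle test would catch. This stands, and it limits how strongly the point can be pressed.

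Third, delayed recognition is inference. Table 2 pools lymphoma and myeloma patients over four schedules, with seven of 44 on 5/2. Section 11.1.12 does describe adverse events on 60 mg 5/2 as comparable to those in the overall trial population, so the symptom argument is weakened rather than removed.

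Fourth, restaging may use MRI instead of CT, so CT exposure is not certain, and a scan might itself reveal an advanced pregnancy. It is not a pregnancy test.

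Fifth, a pre-cycle test can miss a very recent conception, after which a further 15 doses could be given. The change shortens exposure and does not abolish it. The test at the safety visit cannot reduce dosing at all; it serves follow-up of pregnancies conceived around the end of treatment.

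**Conclusion.** The concern holds. Followed exactly, the protocol tests for pregnancy once and then doses without limit of time a drug whose fetal effects it calls unknown. Each unrecognised pregnancy would mean 15 full doses per cycle, 30 by the first restaging, with no test scheduled before the imaging. Expected events are few: about 0.01 to 0.4, up to 0.75 with a year on drug, on the assumed numbers of women, time on treatment and contraceptive failure. How many cycles would pass before recognition is also an assumption. Low frequency keeps this from being essential, but the possible harm is serious and a simple test at existing visits would reduce it, so the change should be made.

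**What to change.** Keep the contraception and self-report rules. For women of childbearing potential, add:

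1. **Section 3.5:** mark beta-HCG in the every-cycle column, and serum beta-HCG in the 1-month column.
2. **Section 3.4:** list serum or urine beta-HCG under "Within three days prior to each treatment cycle", using blood or urine already collected, and done before CT or PET when restaging falls at that time.
3. **Section 3.6.1:** require a negative result before each cycle starts.
4. **Section 3.9:** add serum beta-HCG to the safety visit, on blood already drawn there (no urine is scheduled).

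The cost is a protocol amendment and an inexpensive test in a subset of patients, with no new visit. A false positive could delay a cycle until it is resolved. The safety-visit test may still miss a very recent conception.

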3.6 CRITERIA FOR CONTINUED TREATMENT

3.6.1 Prior to each treatment cycle.

- Treatment with CUDC-907 will continue until progression of disease, development of unacceptable toxicity, or withdrawal of consent.
- Adequate hematologic and organ function:
 - Hemoglobin greater than or equal to 8.0 gm/dL; ANC greater than or equal to 1,000/mm³; Platelets greater than or equal to 75,000/mm³
 - Creatinine \leq 1.5x upper limit of normal (ULN)
 - Total bilirubin \leq 1.5x ULN
 - AST/ALT \leq 2.5x ULN. For subjects with documented liver metastases, the AST/ALT may be \leq 5x ULN.

3.7 RESTAGING

Patients will undergo the following evaluations at the end of every 2 cycles of treatment (+/- 3 days).

- CT scan of the chest, abdomen and pelvis (CT C/A/P) or MRI
- ¹⁸F FDG PET scan will be performed after 2 cycles of treatment (+/- 3 days), and then annually or when clinical indicated.
- Patients who continue to receive clinical benefit may continue treatment at the discretion of the PI.
- Response will be determined using RECIST 1.1 criteria (please see Section 6.4)

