2.2.2 Within 4 weeks prior to treatment

- Brain MRI or CT
- CT scan of the neck, chest, abdomen and pelvis (CT C/A/P) or MRI if patient has renal insufficiency
- Bone scan for patients in whom bone metastases are suspected
- 18-F FDG PET scan

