3 STUDY IMPLEMENTATION

3.1 STUDY DESIGN

This will be an open label, phase II trial and patients will be given 60 mg of CUDC-907 orally once a day on a five days on and two days off schedule (5/2). One cycle will be 21 days. Patients may continue on treatment if there are no unacceptable adverse events (see Section 3.3) or disease progression on anatomic imaging. Response to treatment will be assessed after completing two cycles of treatment.

Patients will undergo ultrasound -guided biopsy of their tumor once before treatment if the site of disease is readily accessible without posing a significant risk to the patient. The tissue sample will be used for mutation profiling of common driver mutations and phosphoprotein profiling of commonly activated pathways in poorly differentiated and anaplastic thyroid cancer, and aggressive variants of differentiated thyroid cancer (**Table 1**).

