6.4.3 Methods for Evaluation of Measurable Disease

All measurements should be taken and recorded in metric notation using a ruler or calipers. All baseline evaluations should be performed as closely as possible to the beginning of treatment and never more than 4 weeks before the beginning of the treatment.

The same method of assessment and the same technique should be used to characterize each identified and reported lesion at baseline and during follow-up. Imaging-based evaluation is preferred to evaluation by clinical examination unless the lesion(s) being followed cannot be imaged but are assessable by clinical exam.

Clinical lesions: Clinical lesions will only be considered measurable when they are superficial (e.g., skin nodules and palpable lymph nodes) and ≥ 10 mm diameter as assessed using calipers (e.g., skin nodules). In the case of skin lesions, documentation by color photography, including a ruler to estimate the size of the lesion, is recommended.

Chest x-ray: Lesions on chest x-ray are acceptable as measurable lesions when they are clearly defined and surrounded by aerated lung. However, CT is preferable.

Conventional CT and MRI: This guideline has defined measurability of lesions on CT scan based on the assumption that CT slice thickness is 5 mm or less. If CT scans have slice thickness greater than 5 mm, the minimum size for a measurable lesion should be twice the slice thickness. MRI is also acceptable in certain situations (e.g. for body scans).

Use of MRI remains a complex issue. MRI has excellent contrast, spatial, and temporal resolution; however, there are many image acquisition variables involved in MRI, which greatly impact image quality, lesion conspicuity, and measurement. Furthermore, the availability of MRI is variable globally. As with CT, if an MRI is performed, the technical specifications of the scanning sequences used should be optimized for the evaluation of the type and site of disease. Furthermore, as with CT, the modality used at follow-up should be the same as was used at baseline and the lesions should be measured/assessed on the same pulse sequence. It is beyond the scope of the RECIST guidelines to prescribe specific MRI pulse sequence parameters for all scanners, body parts, and diseases. Ideally, the same type of scanner should be used and the

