image acquisition protocol should be followed as closely as possible to prior scans. Body scans should be performed with breath-hold scanning techniques, if possible.

Ultrasound: Ultrasound is not useful in assessment of lesion size and should not be used as a method of measurement. Ultrasound examinations cannot be reproduced in their entirety for independent review at a later date and, because they are operator dependent, it cannot be guaranteed that the same technique and measurements will be taken from one assessment to the next. If new lesions are identified by ultrasound in the course of the study, confirmation by CT or MRI is advised. If there is concern about radiation exposure at CT, MRI may be used instead of CT in selected instances.

FDG-PET: While FDG-PET response assessments need additional study, it is sometimes reasonable to incorporate the use of FDG-PET scanning to complement CT scanning in assessment of progression (particularly possible 'new' disease). New lesions on the basis of FDG-PET imaging can be identified according to the following algorithm:

- a. Negative FDG-PET at baseline, with a positive FDG-PET at follow-up is a sign of PD based on a new lesion.
- b. No FDG-PET at baseline and a positive FDG-PET at follow-up: If the positive FDG-PET at follow-up corresponds to a new site of disease confirmed by CT, this is PD. If the positive FDG-PET at follow-up is not confirmed as a new site of disease on CT, additional follow-up CT scans are needed to determine if there is truly progression occurring at that site (if so, the date of PD will be the date of the initial abnormal FDG-PET scan). If the positive FDG-PET at follow-up corresponds to a pre-existing site of disease on CT that is not progressing on the basis of the anatomic images, this is not PD.
- c. FDG-PET may be used to upgrade a response to a CR in a manner similar to a biopsy in cases where a residual radiographic abnormality is thought to represent fibrosis or scarring. The use of FDG-PET in this circumstance should be prospectively described in the protocol and supported by disease-specific medical literature for the indication. However, it must be acknowledged that both approaches may lead to false positive CR due to limitations of FDG-PET and biopsy resolution/sensitivity.

Note: A 'positive' FDG-PET scan lesion means one which is FDG avid with an uptake greater than twice that of the surrounding tissue on the attenuation corrected image.

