6.4.4.3 Evaluation of Best Overall Response

The best overall response is the best response recorded from the start of the treatment until disease progression/recurrence (taking as reference for progressive disease the smallest measurements recorded since the treatment started). The patient's best response assignment will depend on the achievement of both measurement and confirmation criteria.

Target Lesions	Non-Target Lesions	New Lesions	Overall Response
CR	CR	No	CR
CR	Non-CR/Non-PD	No	PR
CR	Not evaluated	No	PR
PR	Non-PD or not all evaluated	No	PR
SD	Non-PD or not all evaluated	No	SD
Not all evaluated	Non-PD	No	NE
PD	Any	Yes or No	PD
Any	PD	Yes or No	PD
Any	Any	Yes	PD

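### The neck is in the baseline CT but is not named in the restaging or off-treatment CT lists, in a trial that enrols locally advanced thyroid cancer; probably a drafting slip, and it should be corrected

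*Combined protocol and SAP*

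**What the plan says.** Section 2.2.2 sets the baseline scan: "CT scan of the neck, chest, abdomen and pelvis (CT C/A/P) or MRI if patient has renal insufficiency". Section 3.7, which governs restaging every two cycles, asks for "CT scan of the chest, abdomen and pelvis (CT C/A/P) or MRI". The same line appears at 3, 6 and 12 months off treatment (3.8.1, 3.8.2, 3.8.3) and at the visit about 30 days after the last dose (3.9). The calendar in 3.5 has a single row for CT of chest, abdomen and pelvis or MRI, ticked at baseline, every two cycles, and at 1, 3, 6 and 12 months.

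Section 1.1.1 makes RECIST response the primary objective, in locally advanced as well as metastatic disease. Section 3.1 ties dosing to the scans: "Patients may continue on treatment if there are no unacceptable adverse events (see Section 3.3) or disease progression on anatomic imaging". Section 6.4.3 states: "The same method of assessment and the same technique should be used to characterize each identified and reported lesion at baseline and during follow-up". Section 6.4.2 adds that the status of each non-target lesion is to be noted throughout follow-up.

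**The concern.** Locally advanced thyroid cancer can have target, non-target or new lesions in the neck. Taken literally, the lists examine that region by CT once, at baseline, and not again. Three things are then at stake:

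- the best overall response of a patient with neck lesions, which is the primary endpoint;
- the date of progression, and so PFS (a secondary objective);
- the decision in 3.1 to keep dosing.

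The response rule in section 8 turns on small counts: 0 against 1 responder in 13, and 2 against 3 in 20. Any small two-stage design has that property, so it is not evidence of a fault here, but it does mean that single classifications matter.

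**Working it through.** **1. Regions named for CT, list by list**

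| Section | When | Regions named |
|---|---|---|
| 2.2.2 | Baseline | Neck, chest, abdomen, pelvis |
| 3.7 | Every 2 cycles | Chest, abdomen, pelvis |
| 3.9 | About 30 days after last dose | Chest, abdomen, pelvis |
| 3.8.1, 3.8.2, 3.8.3 | 3, 6, 12 months off treatment | Chest, abdomen, pelvis |
| 3.5 calendar | All of these | Chest, abdomen, pelvis |

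Five of five post-baseline lists leave out the neck. Their MRI alternative names no region.

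**2. Known neck lesions.** Sections 6.4.2 and 6.4.3 require them to be reassessed, by the same method as at baseline. The list in 3.7 does not provide the scan, so the two parts of the protocol conflict. If the list is followed, the table in 6.4.4.3 gives these results:

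- *Neck target not rescanned.* The targets are not all evaluated. With non-target disease not progressing and no new lesion, the overall result is NE, so a true response can be lost. Section 6.4.1 counts a patient as evaluable once disease has been re-evaluated, without requiring every target site, so this patient could stay in the denominator as a non-responder.
- *Neck non-target not rescanned.* The PR row accepts "Non-PD or not all evaluated", so PR stands although the neck was not checked.

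**3. New neck lesions.** A new lesion is PD under 6.4.4. The same-method sentence in 6.4.3 covers only lesions already identified. The other means of detection are partial:

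- Limited physical examination is due every cycle, but clinical lesions count as measurable only if superficial and at least 10 mm.
- For ultrasound, 6.4.3 says: "Ultrasound is not useful in assessment of lesion size and should not be used as a method of measurement".
- For PET, the calendar footnote says: "18F FDG PET scan will be performed after 2 cycles of treatment (+/- 3 days), and then annually or when clinical indicated". Restaging falls every 2 × 21 = 42 days, so a full first year on treatment has 8 restagings (days 42, 84, ..., 336). PET is scheduled at the first only, which leaves 8 − 1 = 7 without it. Few patients with anaplastic disease would reach that many: the median survival of 4.9 months in section 1.2 is about 149 days, and 149/42 ≈ 3.5, so about three.

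**4. Which list affects what.** Restaging under 3.7 feeds response, PFS and continued dosing. The calendar ticks the RECIST assessment only at baseline and every two cycles, so the scans in 3.8 and 3.9 bear mainly on PFS.

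**5. Illustration of size.** First, the plan's own design (n1 = 13, stop at 0 responders; n = 20, success at 3 or more), by exact binomial:

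- Early stopping at 5%: 0.95^13 = 0.513, as stated in section 8.
- Type I error at 5%: 0.074, within the 0.10 allowed.
- Power at 25%: with X the stage 1 and Y the stage 2 responders (7 patients), P(X=1)·P(Y≥2) + P(X=2)·P(Y≥1) + P(X≥3) = 0.1029 × 0.5551 + 0.2059 × 0.8665 + 0.6674 = 0.903.

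Let f be the share of patients left NE because a neck target was not rescanned. The documents do not give f; 5% to 30%, independent of response, is assumed purely for illustration. If NE counts as non-response, the observable rate is 0.25(1 − f). If NE patients are replaced, 40/(1 − f) must be enrolled to obtain 40 evaluable.

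| f (assumed) | Observable rate | Power | Enrolled for 40 evaluable |
|---|---|---|---|
| 0 | 0.2500 | 0.903 | 40 |
| 5% | 0.2375 | 0.880 | 43 |
| 10% | 0.2250 | 0.854 | 45 |
| 20% | 0.2000 | 0.786 | 50 |
| 30% | 0.1750 | 0.697 | 58 |

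The accrual ceiling in section 8 is 50. The figure of 40 applies only if both cohorts pass stage 1.

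**The case against.** The strongest reply is that this is a wording slip which the protocol already corrects elsewhere. Section 2.2.2 attaches the abbreviation C/A/P to a scan that includes the neck, and the calendar uses one row for baseline and follow-up, so the baseline scan can be read as carried forward. Section 3.7 sends response to section 6.4, which obliges staff to follow known neck targets and non-targets. The NE and unverified-PR results therefore arise only if section 6.4 is disregarded. A new neck lesion may also be felt at the every-cycle examination or seen on PET.

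Most of this stands. It makes a slip the likeliest explanation and shows that neck imaging is not forbidden. It does not remove the inconsistency: the five lists write out three regions in full, and staff working from them would not order a neck scan. For new lesions, section 6.4 supplies no scheduled scan, and examination, calipers and PET fill the gap only in part.

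A reader might infer more than the documents support:

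- *That the sponsor chose to stop imaging the neck.* No text says so, and 6.4.2 and 6.4.3 point the other way.
- *That the trial loses up to 20 points of power, or will exceed its ceiling.* Those figures need an assumed f, which requires a neck target that is neither rescanned despite 6.4.3 nor measurable by caliper. Nothing in the documents supports any value of f.
- *That all five omissions damage the primary endpoint.* Four of the lists are off-treatment and cannot affect continued dosing.
- *That dosing rests on imaging alone.* Section 3.7 allows continuation for clinical benefit at the investigator's discretion, and 3.9.1 allows that discretion to end treatment.

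**Conclusion.** The point holds as an internal inconsistency, probably a drafting slip, and should be corrected. For known neck lesions the list in 3.7 conflicts with 6.4.2 and 6.4.3. For new neck lesions, no scheduled CT or MRI after baseline names the region, so progression can be missed or detected late. The error can run either way: a response lost as NE, or a PR recorded with the neck unchecked.

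The omission in 3.7 touches the primary response endpoint, PFS and continued dosing; those in 3.8 and 3.9 touch mainly PFS. The size cannot be derived from the documents. It is zero wherever the neck is scanned anyway, and the power and enrolment figures above only illustrate what an assumed NE share would do. The Simon design itself reproduces and is not in question. Confidence is medium: the text is clear, but actual scanning practice is unknown.

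**What to change.** In 3.7, 3.8.1, 3.8.2, 3.8.3 and 3.9, name the same four regions as 2.2.2 (neck, chest, abdomen and pelvis), and state that the MRI alternative covers those same regions. Rename the calendar row *CT neck/CAP or MRI*. Section 3.1, the clinical-benefit provision in 3.7, the PET rules and the Simon design can stay as they are.

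The cost is a wording change in five lists and one row, plus one added region, with its radiation and scan time, on scans already scheduled. It needs no extra visits and no extra patients.
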